11.3.2 ECOG Performance Status at Baseline

The ECOG Performance Status will be described from the data collected on the “ECOG Performance Status” eCRF page. It will be described at baseline by the frequency and percentage of participants in each category:

- 0: Fully active, able to carry on all pre-disease performance without restriction.
- 1: Restricted in physically strenuous activity but ambulatory and able to carry out work of a light or sedentary nature, e.g., light housework, office work.
- 2: Ambulatory and capable of all selfcare but unable to carry out any work activities. Up and about more than 50% of waking hours.
- 3: Capable of only limited selfcare, confined to bed or chair more than 50% of waking hours.
- 4: Completely disabled. Cannot carry on any selfcare. Totally confined to bed or chair.
- 5: Dead.

11.3.3 Vital signs at Baseline

The following vital signs at baseline will be collected from the “Vital signs” eCRF page and will be summarized:

- Height (cm)
- Weight (kg)
- Body Mass Index (BMI) (kg/m²)

Height, weight and BMI at baseline will be listed in the demographics listing (see section 11.1, also for BMI computation).

Other vital signs parameters such as systolic and diastolic blood pressure, pulse rate and respiration rate at baseline will be included in the summary tables by timepoint.

11.3.4 Skin status history

Skin status history is collected on the “Skin Status History” eCRF page and will be summarized by the frequency and percentage of participants having the following history of:

- Frequent sunburn (Yes, No, Unknown)
- Easy sunburn (Yes, No, Unknown)
- Skin cancer (Yes, No, Unknown)
- Significant UV exposure (Yes, No, Unknown)
- Photosensitivity due to skin disorder (Yes, No, Unknown)
- Photosensitivity due to medication (Yes, No, Unknown)

- Family history of skin cancer in first degree relative (i.e. parents, siblings and/or children) (Yes, No, Unknown)
- Number of participants having history of the skin conditions above (No condition, 1 condition, 2 conditions, 3 or more conditions)

A listing of skin status history will be provided.

11.3.5 PD-L1 test

All tests collected on the “PD-L1 Tumor Testing” eCRF page will be summarized. This includes the Roche Ventana PD-L1 SP142 assay and other testing. All tests will be described using the following categories: positive, negative, not evaluable (NE) or other.

Listing will also be provided and include: participant identifier, age, sex, race, visit, collection date, date of PD-L1 testing, unique sample identifier, test performed (SP142 assay or other), result (positive, negative, NE or other), tissue used (specimen type and location), if testing performed for clinical trial inclusion, if there is membrane tumor cell staining (% of tumor cell stained), if there is immune cell staining (staining score) and if the combined tumor cell and tumor associated immune cells score available (score). This listing will be sorted by participant identifier.

At the end of the study, retrospective testing on tumor samples will be performed by a central lab. Analyses to be done are described in section [16.4](#).

11.3.6 HIV testing

The result from HIV testing will be reported in a listing, including participant identifier, age, sex, race, test performed, test name, testing date and result. This listing will be sorted by participant identifier.

11.3.7 Tumor Biopsy

Tumor biopsy is collected on the “Tumor Biopsy (Block or Slides)” eCRF page, a listing of tumor biopsy will be provided including: participant identifier, age, sex, race, visit, collection date, sample type (fresh biopsy or archival tissue sample), sample identifier, sample type for tumor block and for tumor tissue the number of slides collected. In case tumor is assessed as not evaluable for HMGA2 expression by the central laboratory, if an additional tumor specimen has been submitted, its date of collection and additional specimen ID will be displayed. This listing will be sorted by participant identifier and collection date.

11.4 Prior Anticancer Therapy

The prior anti-cancer therapies are collected under the “Prior Anti-Cancer Drug Therapies Details” and “Prior Anti-Cancer Surgeries Details” eCRF pages.

The number and percentage of participants in each of the following anti-cancer therapy categories will be tabulated:

- Participants with at least one type of prior anticancer treatment or procedure (i.e. drug therapy, radiotherapy or procedure)
- Participants with at least one prior anticancer drug therapy
- Participants with at least one prior anticancer radiotherapy
- Participants with at least one prior anticancer surgery

Prior anticancer drug therapy will be summarized as follows based on the number and percentage of participants with the following:

- Number of prior lines of therapy for metastatic/locally advanced disease: 0 / 1 / 2 / 3 / ≥ 4
- Intent of Therapy: Neoadjuvant / Adjuvant / Metastatic or Locally advanced
- Time since documented progression disease while receiving prior anticancer drug therapy.
- Best response of last treatment regimen: Complete Response (CR) / Partial Response (PR) / Stable Disease (SD) / Progressive Disease (PD) / Non-Complete Response/Non-Progressive Disease (Non-CR/Non-PD) / Not evaluable / Unknown. Best response of last treatment regimen will be identified based on previous anticancer drug therapies with non-missing start date.

The percentages of prior anticancer drug therapies will be based on the number of participants who had received at least one previous anticancer drug therapy regimen.

Additionally, separate listings for prior anticancer drug therapies, radiotherapy and surgeries will be displayed. These listings will include the participant identifier, age, sex, race and all the relevant collected data-fields on the corresponding eCRF pages as follows:

- For drug therapies: regimen ID, PT, medication name, start date, end date, intent of therapy, best response and date of progression . This listing will be sorted by participant identifier, regimen ID, start date, end date (note that missing end date will be considered as ongoing and will be displayed after non-missing date in case of same start date) and PT.
- For radiotherapies: record ID, stat and stop dates and location of radiotherapy. This listing will be sorted by participant identifier, record ID, start date and end date (note that missing end date will be considered as ongoing and will be displayed after non-missing date in case of same start date).
- For surgeries: date of surgery, name and location of surgery, curative intent of surgery (Y/N), and outcome of surgery. This listing will be sorted by participant identifier, date of surgery and name of surgery.

12

Previous or Concomitant Medications/Procedures

Analysis Set: FAS

CONFIDENTIAL
INFORMATION

30/69
30/70

CCI
CCI

12.1

Previous and concomitant medications

Previous medications are medications, other than study treatment and pre-medications for study treatments, which started before first administration of study treatments.

Concomitant treatments are medications, other than study treatment, which are taken by participants any time during the on-treatment period (see section 9.8).

A medication may be classified as both concomitant and previous. The respective flags will be derived based on start and end date.

Concomitant and previous treatment each will be summarized by number and percentage of participants from the “Concomitant Medication Details” eCRF. ATC-2nd level and PT will be tabulated as given from the WHO-DD dictionary most current version at the time of the database lock. If any previous or concomitant medication is classified into multiple ATC classes, the medication will be summarized separately under each of these ATC classes. The summary tables will be sorted by decreasing frequency of drug class and decreasing frequency of drug name in a given drug class. In case of equal frequency regarding drug class (respectively drug name), alphabetical order will be used. In case any specific medication does not have an ATC classification level 2 coded term, it will be summarized under “Unavailable ATC classification” category. Each participant will only be counted once, even if he/she received the same medication at different times.

Specific rules will be used to define if a medication/procedure is considered as a previous, concomitant or both previous and concomitant medication/procedure as detailed in section 9.9.

Previous and concomitant medications will be presented in listing and will include: participant identifier, age, sex, race, PT, medication name as provided by the Investigator, start date, end date, dose, dose units, frequency, route, reason for the medication. This listing will be sorted by participant identifier, start date, end date (note that missing end date will be considered as ongoing and will be displayed after non-missing date in case of same start date) and PT.

12.2

Premedications prior to bintrafusp alfa administration

Premedications are medications administered per protocol on the same day as, but prior to, the study intervention to mitigate potential infusion-related reactions.

As per protocol, premedication prior to bintrafusp alfa administration is optional and at the discretion of the Investigator. If Grade ≥ 2 IRRs are seen during the first 2 infusions, premedication should be continued/implemented for future infusions.

Participants receiving premedication during the study will be summarized for each treatment visit based on “Premedication Bintrafusp Alfa Details” eCRF page. Percentages will be calculated on the number of participants who received an infusion at the associated visit.

Additionally, a listing will be provided including: participant identifier, age, sex, race, medication name, visit, date/time of study intervention, dose, dose units, and route. Premedications occurring

after reinitiation of treatment will be flagged. This listing will be sorted by participant identifier, date and time of administration and medication name.

12.3 Concurrent procedures

Concurrent procedures are reported according to the “Concomitant Procedures Details” eCRF page.

A listing will be provided including: participant identifier, age, sex, race, name of procedure (as provided by the Investigator), start date, end date, indication, reason for procedure and type of specimen collected. A flag will be displayed to identify each procedure as prior to treatment and on-treatment. In case the procedure has been conducted during the reinitiation phase it will also be flagged. This listing will be sorted by participant identifier, start date, end date (note that missing end date will be considered as ongoing and will be displayed after non-missing date in case of same start date) and procedure name.

12.4 Subsequent anticancer treatments and procedures

Anticancer therapy after end or discontinuation of study treatment will be summarized according to “Anti-Cancer Treatment After Discontinuation Details” for anticancer drug therapies, “Radiotherapy After Discontinuation Details” and “Surgery After Discontinuation Details” eCRF pages. The earliest date of start of new anti-cancer drug therapy will be used for the definition of the on-treatment period and the earliest date of start of new anti-cancer therapy will be used for censoring for efficacy analyses.

The number and percentage of participants in each of the following anticancer treatment categories will be tabulated:

- Participants with at least one subsequent anticancer treatment (i.e. drug therapy, radiotherapy or surgery)
- Participants with at least one subsequent anticancer drug therapy
- Participants with at least one subsequent anticancer radiotherapy
- Participants with at least one subsequent anticancer surgery

If collected in the eCRF, the best response of first subsequent anticancer drug therapy will also be described (Complete Response (CR) / Partial Response (PR) / Stable Disease (SD) / Progressive Disease (PD) / Non-Complete Response/Non-Progressive Disease (non-CR/non-PD) / Not Evaluable / Unknown).

In addition, the anticancer treatment after discontinuation of study treatment will be provided in two listings:

- For medication: participant identifier, age, sex, race, PT/medication name, regimen name, start date, end date, route and best response (if collected in the eCRF). This listing will be sorted by participant identifier, start date, end date, PT/medication name and regimen name.

For radiotherapy and surgery: participant identifier, age, sex, race, start date, end date, radiotherapy site or name of surgery/location. For surgery only: outcome and was the surgery curative in intent (Y/N).

13

Study Treatment: Compliance and Exposure

Analysis set: SAF

Participants will receive an intravenous infusion of bintrafusp alfa at a dose of 1200 mg over 1 hour (-10 minutes/+ 20 minutes, i.e., over 50 to 80 minutes) once every 2 weeks as detailed in the Table 1 in the study protocol, until confirmed disease progression (PD), unacceptable toxicity, or occurrence of any criterion for withdrawal from the study.

All dosing calculations and summaries will be based on “Bintrafusp Alfa Administration Details” eCRF page. Data collected during the treatment reinitiation phase will be included in the summary statistics and described in listings.

For the analysis of exposure, a dose is regarded to be administered if the actual dose received is > 0 mg.

Imputation for incomplete start and end dates of study treatments are described in section 9.9.

The **duration** of bintrafusp alfa treatment in weeks during the study is defined as:

$$\text{Duration of treatment (weeks)} = \left(\frac{\text{date of last dose} - \text{date of first dose} + 14}{7} \right)$$

The **cumulative dose** overall of bintrafusp alfa per participant is the sum of the actual dose that the participants received during the study (i.e., total dose administered [mg]).

The **dose intensity** of treatment (DI) (mg/week) of bintrafusp alfa during the study is defined as:

$$\text{DI of treatment (mg/week)} = \left(\frac{\text{Cumulative dose of treatment (mg)}}{\text{Duration of bintrafusp alfa treatment (weeks)}} \right)$$

The **relative dose intensity** (RDI) is defined as the actual dose intensity divided by the planned dose intensity during the study and expressed in percentage:

$$\text{RDI of treatment (\%)} = 100 \times \left(\frac{\text{DI of treatment (mg/week)}}{\text{planned dose level (mg/week)}} \right)$$

The following summary tables will be provided:

- Duration of therapy (weeks)
- Total number of infusions received
- Cumulative dose (mg)

- Dose intensity (mg/week)
- Relative dose intensity (%) as continue variable, and categorized as:
 - < 80%
 - 80%-90%
 - > 90%

Two listings will be presented:

- A listing of study intervention which will provide: participant identifier, age, sex, race, visit, infusion start date and time, infusion end date and time, infusion rate (mL/hr), actual dose (mg), route, administration modification and reason for modification, change in administration detail, treatment delay (days). Data collected during the treatment reinitiation phase will be flagged.
- An additional listing of treatment exposure and compliance which will include participant identifier, age, sex, race, duration of therapy (weeks), total number of infusions received, cumulative dose of therapy (mg), dose intensity (mg/week), and relative dose intensity (%).

Dose Modification

Dose modification is not allowed per protocol. No summaries will be provided.

Infusion Rate Reductions

Infusion rate reductions as recorded on the “Bintrafusp Alfa Administration Details” eCRF page will be used for analysis. Number of participants with at least one infusion rate reduction, reason for infusion rate reductions (adverse event or other), as well as a categorization of the number of infusion rate reductions (1 / 2 / ≥ 3) will be summarized.

Therapy Delays

Delays of therapy can be calculated only for participants having at least two treatment administrations. It will be derived for each infusion as the number of days since last infusion – 14:

$$\text{Therapy delay} = \text{start date of current infusion} - \text{start date of the previous infusion} - 14$$

If the result is > 0 day, then this will be classed as a delay. A participant may have more than one treatment delay throughout the course of treatment.

The following will be summarized in a table:

- Number of participants with at least one delay
- Number of participants with no delay
- Number of delays per participant (1 delay, 2 delays, 3 delays, ≥ 4 delays)
- Longest delay per participant (1-2 days, 3-8 days, 9-15 days, ≥ 16 days)

Infusion Temporary Interruptions

Study drug infusion temporarily interrupted as recorded on the “Study Treatment Administration Details” page of the eCRF will be used for analysis. Number of participants with at least one study drug temporary interruption, reason for study drug temporary interruption (adverse event or other), as well as a categorization of the number of study drug temporary interruptions (1 / 2 / ≥ 3) will be summarized.

14 Efficacy Analyses

Analysis Set: FAS

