- Drug must not be given to a known pregnant participant (see Appendix 3).
- Use of a prohibited concomitant drug, as defined in Section 6.5.2, where the predefined consequence is withdrawal from the study intervention.

In case of discontinuation from the study intervention:

- The day of End-of-Treatment Visit will correspond to the day of withdrawal (or within 7 days).
- An attempt should be made to perform all assessments scheduled for the End-of-Treatment Visit if possible. If not possible, the most clinically relevant assessments and appropriate eCRFs for the End-of-Treatment Visit should be prioritized as feasible.
- Participants will be asked to continue Safety Follow-up and Survival Follow-up, which includes the collection of data on survival, and subsequent anticancer therapy. After completion of the follow-up period or after the End-of-Treatment Visit, whichever is applicable, the appropriate eCRF section for Study Termination must be completed.
- If the participant is enrolled into a new study or any new therapy post-withdrawal from study intervention, the Safety Follow-up Visit should be scheduled prior to the start of the new treatment irrespective of the 28-day Safety Follow-up period.

The Schedule of Activities specifies the data to collect at study intervention discontinuation and follow-up, and any additional evaluations that need to be completed.

7.1.1 **Temporary Discontinuation**

See Section 6.8 and Section 6.9 for guidance on temporary discontinuation from study intervention.

7.1.2 **Rechallenge**

7.1.2.1 **Reinitiation**

One reinitiating course of treatment at the same dose and schedule and treatment duration up to 24 months is allowed at the discretion of the Investigator and agreement of the Medical Responsible for:

- Participants who are experiencing SD, PR, or CR at the time of discontinuation, and then subsequently develop disease progression after stopping therapy, but prior to the End of the Study.

OR

- Participants who are discontinued due to an AE that are subsequently well managed or resolved after stopping therapy, but prior to the End of the Study.

The participant should reinitiate treatment at the treatment phase visit where they left off according to the Schedule of Activities (Table 1). Participants who reinitiate treatment should stay on study and should be treated and monitored according the Schedule of Activities for the rest of the study.

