A listing containing participant disposition information will be displayed, including all participants (i.e. including screening failures, but not re-screened participants (at their screen failure time) which will be listed in a specific listing). The listing will include the following information: participant identifier, date of informed consent, included in the study (if not reason for exclusion), first/last study intervention date, date and reason off-treatment, date and reason off-study, population flags. If the reason for exclusion from trial, off-treatment or off-study are categorized as “Other, specify” or “Withdrew consent from treatment, specify”, the verbatim text as entered in the eCRF will be presented in the listing. This listing will be sorted by participant ID.

In addition, a listing of participants for which study treatment has been reinitiated will be provided with the following information: participant identifier, date of first study intervention, date of last study intervention, reason for treatment termination, date of last reinitiation of study treatment administration date and status at end of treatment reinitiation including reason for treatment discontinuation, as applicable. If the status at end of treatment is categorized as “Other, display the verbatim text as entered in the eCRF. This listing will be sorted by participant ID.

If any re-screened participants are observed, they will be presented in a specific listing which will include: participant identifier (identifier at inclusion in the study), date of informed consent at inclusion, date of first study treatment administration, initial participant identifier (identifier at screen failure), date of informed consent at screen failure, date and reason of screen failure. Note in case participants have been screened several times, all screening attempts will be listed. This listing will be sorted by participant ID.

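### SAP section 13 counts the off-drug interval before a reinitiated course as treatment duration and as a therapy delay, so RDI falls below 100% even when no infusion was missed

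*SAP*

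**What the plan says.** Protocol section 7.1.2.1 (Reinitiation): "One reinitiating course of treatment at the same dose and schedule and treatment duration up to 24 months is allowed". Two routes qualify: stopping in SD, PR or CR and progressing later, or stopping for an AE that has since been managed or has resolved. On timing: "The participant should reinitiate treatment at the treatment phase visit where they left off". Protocol section 9.4.2 leaves the summary of reinitiation data to the analysis plan.

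SAP section 13 (Study Treatment: Compliance and Exposure): "Data collected during the treatment reinitiation phase will be included in the summary statistics and described in listings". Cumulative dose is the total received in the study. Duration in weeks is (last dose date − first dose date + 14)/7. DI is cumulative dose over duration, and RDI is DI over the planned weekly dose. Delay is "derived for each infusion as the number of days since last infusion", less 14, and any positive result counts as a delay. The longest delay is categorised, with 16 days or more at the top; RDI is categorised as below 80%, 80% to 90%, and above 90%.

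Section 13 specifies two listings. The study intervention listing carries the delay in days and flags reinitiation data. The exposure and compliance listing carries identifiers and "duration of therapy (weeks), total number of infusions received, cumulative dose of therapy (mg), dose intensity (mg/week), and relative dose intensity"; no reinitiation flag or gap column is named for it.

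SAP section 10.1 treats the first stop as a termination. Its listing of reinitiated participants gives the "reason for treatment termination, date of last reinitiation of study treatment administration date".

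**The concern.** Section 10.1 records that treatment ended and later restarted; section 13 counts the weeks between as treatment. RDI is meant to compare what was given with what was planned, but the planned 600 mg/week is applied to weeks in which the protocol scheduled no infusion. The schedule resumes at the visit where it stopped, so no infusion visit was passed over, although follow-up and tumour assessments continue.

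A participant who received every scheduled infusion in both courses would thus be listed with an RDI below 100%, and the first infusion of the second course would carry a long delay. The plainest case is a participant who stops in response at the planned 24 months and reinitiates after progression: a planned stop becomes a therapy delay. What is at stake is the accuracy of derived exposure values for individual participants.

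**Working it through.** The documents state no duration, DI or RDI figure to reproduce, so the formulas were first checked on a single course.

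**Inputs from the documents.** 1200 mg every 2 weeks, that is 1200/2 = 600 mg/week; the section 13 formulas above.

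**Assumptions.** Infusions exactly 14 days apart within each course, none missed. Course and gap lengths are not given in the documents and are assumed. The gap runs from 14 days after the last first-course dose to the first dose of the second course.

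**Check on one course.** Twelve infusions, Day 1 to Day 155: (155 − 1 + 14)/7 = 24 weeks; 14,400 mg; 600 mg/week; RDI 100%; no delay. The formulas work for one course.

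**Two 12-infusion courses, 24-week gap.**
- Second course starts on Day 155 + 14 + 168 = 337 and ends on Day 491.
- Duration: (491 − 1 + 14)/7 = 72 weeks.
- Dose: 24 × 1200 = 28,800 mg. DI: 28,800/72 = 400 mg/week. RDI: 400/600 = 66.7%.
- Delay at the first infusion of the second course: 337 − 155 − 14 = 168 days.
- Implied planned dose: 72 × 600 = 43,200 mg. The excess of 14,400 mg equals 12 infusions that were never scheduled.

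**General form.** With no missed infusion, RDI = on-drug weeks/(on-drug weeks + gap weeks).

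| Courses (infusions) | Gap (weeks) | Listed duration (weeks) | DI (mg/week) | RDI | Delay (days) |
|---|---|---|---|---|---|
| 12 + 12 | 4 | 52 | 553.8 | 92.3% | 28 |
| 12 + 12 | 12 | 60 | 480.0 | 80.0% | 84 |
| 12 + 12 | 24 | 72 | 400.0 | 66.7% | 168 |
| 52 + 12 | 12 | 140 | 548.6 | 91.4% | 84 |

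RDI falls below 90% once the gap exceeds one ninth of on-drug time, and below 80% once it exceeds one quarter. For 48 weeks on drug these limits are 5.3 and 12 weeks. Any gap of 16 days or more reaches the top delay category.

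**Alternative reading of last dose.** Section 13 does not define it for reinitiated participants; SAP section 15.2.1 (Deaths) uses the last dose of the reinitiation phase. Taking the last first-course dose instead does not help: 28,800 mg over 24 weeks is 1200 mg/week, an RDI of 200%.

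**Summing duration over courses.** 24 + 24 = 48 weeks; 28,800/48 = 600 mg/week; RDI 100%, whatever the gap.

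**The case against.** The strongest reply is that this is a convention. Section 13 defines its quantities over the study and says openly that reinitiation data are included; SAP section 9.8 also uses one span, and the protocol leaves the handling to the SAP. The whole-span value also has a merit: it does not depend on how a gap is labelled. An 8-week AE gap within 24 infusions gives 48/56 = 85.7% under the SAP rule however it is recorded. Per-course RDI gives 85.7% if it is recorded as a hold and 100% if recorded as discontinuation plus reinitiation. After an AE discontinuation, a low whole-span RDI tells the reader that dosing was interrupted. That stands, and it is why the whole-span value should be kept. It does not rescue the rule for participants who stopped in SD, PR or CR and reinitiated on progression.

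It also stands that the delay sits in the study intervention listing, where reinitiation data are already flagged, so a reader can recognise it. The unflagged values are duration, DI and RDI in the exposure and compliance listing. Even there, the gap can be reconstructed from the other listings.

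A reader might infer that the single-span on-treatment period in SAP section 9.8 is wrong too. The documents do not support that: it is an explicit choice that matches Protocol section 9.4.2. A reader might also take very short courses as typical, since the median in the Phase I TNBC cohort was 3 doses. That figure describes a whole cohort, not reinitiators. Three on-schedule infusions end on Day 29, before the first scheduled post-baseline scan on Day 57, so such a participant most plausibly stopped for an AE, where the whole-span value is informative.

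**Conclusion.** Section 13 as written gives misleading duration, DI, RDI and delay values for a participant who reinitiates treatment. For two fully dosed 12-infusion courses, RDI is 92.3%, 80.0% or 66.7% for assumed gaps of 4, 12 or 24 weeks, and would be 100% if duration were summed over courses. The direction follows from the formulas; the size depends wholly on course and gap lengths that the documents do not give. The distortion is clearest on the route of SD, PR or CR followed by progression.

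The point is minor. Only reinitiating participants are affected, and there may be none. Under SAP section 4.1 exposure is not among the analyses dropped by name, but listings replace summary tables as judged appropriate, so the RDI and delay categories may never be tabulated. A reader might infer that safety or efficacy results are biased. The documents do not support that: efficacy is not to be analysed, and SAP section 15 specifies no safety analysis that uses DI or RDI.

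**What to change.** In SAP section 13:
- derive duration as the sum over courses of (last dose − first dose + 14)/7, and base DI and RDI on it;
- compute therapy delays within a course only;
- add to the exposure and compliance listing a reinitiation flag and the off-drug interval, with the reason for treatment termination;
- keep the whole-span RDI as a labelled supplementary value, so that a gap after an AE stays visible.

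Leave SAP section 9.8 and Protocol section 9.4.2 unchanged. The cost is a few lines of text and a little programming: infusion dates, the reinitiation flag and the termination reason are already specified for other listings, so no new data and no protocol change are needed. The downside is two RDI values for reinitiating participants.
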